Difficulties in Emotion Regulation Scale (DERS): The DERS [45] is a 36-item instrument that assesses typical levels of emotion dysregulation across six domains (awareness, nonacceptance, strategies, goal oriented behaviors, impulsivity, and emotional clarity). Participants respond on a Likert scale ranging from 1 (almost never) to 5 (almost always). In the original measure development paper, the DERS was found to have high internal consistency ($\alpha = .93$), good test-retest reliability ($r = .88$, $p < .01$), and adequate construct and predictive validity. The total score is a sum of all items (some reversed). Higher scores indicate more dysregulation. In the present study, Cronbach's alpha at intake was .84, indicating acceptable internal consistency.

Misophonia Questionnaire (MQ). The MQ is a three-part assessment of the types of misophonic sounds the participant is sensitive to and the symptoms experienced. Part one is an 8-item scale that assesses the participant's sensitivity in comparison to others of seven common misophonic triggers and one item for "other." The items use a 5-point Likert scale to identify to what degree the participant is sensitive to each, ranging from 0 (not at all true) to 4 (always true). Part two is completed only if the participant scores a 1 (rarely true) to any of the items in part one. Part two is an 11-item scale that assesses the frequency of ten reactions and one "other" reaction by the participant once they are aware of the misophonic sounds from part one. The items use a 5-point Likert scale to identify the frequency of each reaction, ranging from 0 (never) to 4 (always). Part three is a 15-point self-rating scale of sound sensitivity. There are 5 items with 3 points associated with each with responses ranging from 1-3 (minimal within range of normal or very mild sound sensitivities) to 13-15 (very severe sound sensitivities). Previous studies using the MQ have reported strong reliability and evidence of construct validity [1]. In the present study, Cronbach's alpha was .85 for part I and .92 for part II, indicating acceptable internal consistency.

Subjective Units of Distress Scale (SUDS). During the MRI sessions, neurostimulation session, at

follow-up, and during the ambulatory assessment, we asked participants to rate their current distress on a scale from 0 – no distress to 9 – extreme distress [48].

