The experimental session (Figure 2C) included a 180s pre- session baseline, followed by three experimental runs, one using HF-rTMS over the right DLPFC (39 trains), one using continuous LF-rTMS over the right mPFC, and one using sham rTMS applied over one of those two targets, in a randomized order. Each run included a pre-task baseline (180s), a habituation period (180s) where neurostimulation was administered while the participant was not given any instruction, a sound task, including 5 blocks (600s), and a 600s break. Neurostimulation was administered throughout the sound task. Each block (120s long) started with an instruction (downregulate or listen) and was followed by four sounds played on repeat for 25 seconds (either misophonic, neutral, or aversive depending on the block). Sound and block order was randomized within each run. During the sound presentation a downward arrow (for downregulate), or wave symbol (~, for listen) was present on the screen to guide participants on what to do, neurostimulation and psychophysiological data collection was ongoing.

Psychophysiological Data

HR and GSR were recorded during the whole duration of the sound task and the neurostimulation session. AcqKnowledge software was used to collect and pre-process raw ECG data by using a built in automated heart rate variability (HRV) analysis tool that follows established frequency domain algorithm guidelines [75]. For each baseline, habituation, and 120s listen or down-regulate block, high frequency HRV (HF-HRV) was extracted to capture emotion regulation. Reactivity to emotional cues was captured through GSR. For each baseline, habituation period, and for each sound presentation we extracted the maximum GSR value as a measure of peak emotional arousal. We then removed from the GSR signal, with the help of a MATLAB program, skin conductance responses (SCRs) by leveling the signal when clear spikes were identified [76]. In this way, the tonic signal, or skin conductance level (SCL), was also extracted from each baseline, habituation to rTMS, and 120s listen/regulate block. SCL values represent average arousal during these distinct time periods.

7. Statistical Analyses

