To compare the effects our neurostimulation conditions, we conducted four analyses examining SUDS, peak GSR (SCR; peak arousal), SCL (tonic arousal), and HF-HRV. For the SUDS analyses, we examined the difference between SUDS at the end of each sound and the baseline SUDS collected after the task baseline. If task baseline SUDS were missing, session baseline SUDS were utilized instead. For the SCR analysis, the maximum value of the GSR during the presentation of each sound was used as outcome. For those two variables, the experimental group was used as a between-subject variable (misophonic or emotion dysregulation), and the experimental neurostimulation condition (active HF-rTMS over the right DLPFC, active LF-rTMS over the mPFC- insula, sham rTMS), the block instruction (downregulate misophonic, downregulate aversive, hear misophonic, hear aversive, hear neutral), the order effect of the 3 neurostimulation condition time within the task (0-2, corresponding with the runs employed), within the run (0-4, corresponding to each block), and within the block (0-3, corresponding to each of the sounds played), were used a within-subject variable. The experimental group by neurostimulation condition by block instruction interactions were entered as effects in the SUDS and SCR analyses. For SCR, the maximum GSR value during the habituation period was also controlled for. For the SCL and HF-HRV analyses, the experimental group and neurostimulation condition, and block instruction were also used but only the average within each block was used as outcome, time within block was excluded because HF-HRV requires at least 120s to be accurately assessed, and baseline values were added as main effects, time was considered a categorical variable. To account for multiple comparisons, we used a Bonferroni correction, and dropped the significance threshold to .0125. Differences between LF and HF rTMS were not hypothesized, but explored where both stimulation conditions were different than sham.

Planned covariates for all analyses included coil-to-cortex distance- given evidence that higher distance may impede the effectiveness of neurostimulation interventions for emotion regulation that are not designed to account for this parameter [77,78] - and data-driven covariates were also examined and added to these analyses as needed. Effect sizes were computed by using Feingold's formula [79] and interpreted using Cohen's specifications [80].

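### SUDS is analysed as a change from one run-level rating with no baseline covariate, which costs precision (not validity) in the active-versus-sham comparisons

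*Combined protocol and SAP*

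**What the plan says.** All references are to the combined protocol and SAP.

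- **SUDS outcome (section 7, Statistical Analyses):** "we examined the difference between SUDS at the end of each sound and the baseline SUDS collected after the task baseline". A gap is filled as follows: "If task baseline SUDS were missing, session baseline SUDS were utilized instead".
- **SUDS model terms (section 7):** group, stimulation condition, block instruction, the order and time terms, the three-way interaction, and coil-to-cortex distance. Baseline SUDS is not named.
- **The other three analyses (section 7):** for SCL and HF-HRV, "baseline values were added as main effects". The SCR model controls for the GSR peak during habituation. No reason is given for treating SUDS differently.
- **Status (section 7):** SUDS is a secondary outcome. It is also one of four neurostimulation analyses tested at .0125.
- **Scale (section 3, Measures):** participants were asked "to rate their current distress on a scale from 0 – no distress to 9 – extreme distress".
- **Run structure (section 6, TMS experiment):** every run opens with its own baseline, then habituation under stimulation, then five blocks of four sounds. Stimulation condition changes only between runs.
- **Order (section 5, Randomization):** the sequence of conditions was randomised for each participant.

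**The concern.** A single rating is noisy. When it is subtracted from every score in a run, its error is common to all of them, and averaging over sounds cannot reduce it. Stimulation condition also varies only between runs, so that error falls on the comparison of each active condition with sham. A change score fixes the weight on baseline at one. A covariate lets the data choose the weight, and the plan already does this for two of the other outcomes.

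At stake is the precision of the active-versus-sham comparisons, overall and within a block type, for the only self-reported distress measure among the four analyses. There are 54 participants (27 per group) and the threshold is .0125, so avoidable noise is worth removing.

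**Working it through.** The plan gives no figure to reproduce here. It states no SUDS standard deviation, correlation or power, and the sample-size statement in section 1 rests on AIC response.

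**1. How many scores share one baseline.** 5 blocks × 4 sounds = 20 per run (section 6). The baseline rating is read as preceding stimulation, because the baseline period is listed before habituation.

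**2. Which contrasts carry the baseline.** Let y be a post-sound rating and b the run's baseline.

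- Two blocks in the same run: (y₁ − b) − (y₂ − b) = y₁ − y₂, so b cancels.
- Condition by instruction is a difference of such within-run differences, and the three-way interaction is a difference of those between groups. With complete data b cancels from both.
- Active versus sham, overall or within one block type: (ȳ_active − ȳ_sham) − (b_active − b_sham), so b remains.
- Group comparisons also retain b.

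**3. Why averaging does not help.** Suppose every rating has the same independent error variance e. The error variance of a run-mean change is e(1 + 1/20), of which the baseline supplies 1/1.05 = 95%. For a four-sound block mean it supplies 1/1.25 = 80%.

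**4. Cost relative to adjustment.** Let σ² be the within-person, run-level variance of mean in-task SUDS, k the ratio of the baseline SD to σ, and ρ their correlation.

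- Change score: σ²(1 + k² − 2ρk).
- Baseline-adjusted: σ²(1 − ρ²).
- Difference: σ²(k² − 2ρk + ρ²) = σ²(k − ρ)², which is never negative.

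Neither ρ nor k is in the documents, so a range is shown:

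| k | ρ | Variance ratio | Standard error larger by |
|---|---|---|---|
| = ρ | any | 1.00 | 0% |
| 0.7 | .5 | 0.79/0.75 = 1.05 | 2.6% |
| 0.5 | .2 | 1.05/0.96 = 1.09 | 4.6% |
| 1 | .8 | 0.40/0.36 = 1.11 | 5% |
| 1 | .5 | 1.00/0.75 = 1.33 | 15% |
| 1 | .2 | 1.60/0.96 = 1.67 | 29% |
| 1.5 | .5 | 1.75/0.75 = 2.33 | 53% |

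A k above 1 arises if one rating is noisier than a mean of 20. A k below 1 arises if resting ratings vary less between runs than ratings made during the sounds.

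**5. Simulation check.** Settings: 54 participants, 3 runs, 20 ratings per run, values rounded and clipped to 0-9, assumed SDs of 1.5 between and 1.5 within person, 2,000 replicates, no true condition effect. Single ratings within a run were correlated .3, .5 or .7. This is a different parameter from ρ above, so these results do not calibrate the table.

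- The mean change-score estimate was within 0.005 of zero in every case.
- Within-run contrasts were identical with and without subtraction.
- At a single-rating correlation of .5, the standard error of a whole-run condition contrast was 0.207 for the change score and 0.148 with adjustment.

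**The case against.** The strongest reply is that a change score is a recognised use of baseline and that different handling across outcomes is not itself an error. That is fair. The change score even beats ignoring baseline when k < 2ρ. It cannot beat adjustment, apart from the one or two degrees of freedom spent.

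Four stronger readings are tempting, and the documents do not support them.

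- **That the active-versus-sham estimates are biased.** Order was randomised, so chance differences in run-start distress are sampling noise.
- **That every SUDS test is affected.** The interaction entered in the model is free of the shared baseline when data are complete.
- **That a sizeable loss is certain.** With k and ρ unknown, the range starts at no loss.
- **That the bounded scale calls for this change.** A baseline of b does confine each change to between −b and 9−b. But the post-sound rating has the same ceiling, a linear covariate does not remove it, and no baseline SUDS values are reported. The section 7 normality statement is coarse, but it gives no sign of strong compression at the limits.

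The allowance in section 7 for data-driven covariates might have brought baseline SUDS into the model, but the text does not say so. Baselines in runs 2 and 3 follow earlier stimulation, so they could carry some of its effect. The change score subtracts the same ratings, so it does not avoid this.

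Two objections change the remedy. The study ran until May 2022 and the document is dated March 2023, so a new model is a later addition. The fallback baseline also has to be dealt with, since one session rating could serve more than one run.

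**Conclusion.** The point holds as a cheap gain in precision for a secondary outcome. SUDS is the only one of the four neurostimulation analyses with no named baseline or habituation covariate, and no reason is given. The direction is certain, because the variance difference is σ²(k − ρ)². The size is not: over the values shown, the variance ratio runs from 1.00 to 2.33 (standard error 0% to 53% larger), and both parameters are assumptions. The loss is confined to comparisons of stimulation conditions, overall or within a block type. For the non-randomised group comparison the choice is not one of precision alone, because the change-score and adjusted contrasts can answer different questions. Nothing here makes the planned SUDS analysis invalid.

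**What to change.** - Add the run's task-baseline SUDS to the SUDS model as a covariate, split into the participant's mean baseline and the run's deviation from it. Use it for the active-versus-sham contrasts.
- For runs that rely on the session-baseline fallback, either enter that value with an indicator or exclude those runs in a sensitivity analysis. State how many runs are involved.
- Label the adjusted model as added after the study ended, and report it beside the planned change-score analysis.
- Keep the unadjusted change score for the misophonia-versus-control comparison.
- If baseline SUDS was in fact among the data-driven covariates, say so.

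The cost is a refit on ratings already collected, one or two extra coefficients (plus the fallback indicator if used), and two SUDS results to report instead of one.

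### The outcome labelled SCR is a raw peak conductance that keeps condition-linked tonic change within a run, so it does not isolate the skin conductance response

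*Combined protocol and SAP*

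**What the plan says.** The Psychophysiological Data part of section 6 gives the purpose of the signal: "Reactivity to emotional cues was captured through GSR". For each baseline, habituation period and sound, "we extracted the maximum GSR value as a measure of peak emotional arousal". Only after that step does a MATLAB routine remove "skin conductance responses (SCRs) by leveling the signal when clear spikes were identified". The cleaned trace has one stated use: "In this way, the tonic signal, or skin conductance level (SCL), was also extracted from each baseline", and likewise from each habituation period and each 120 s block.

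Section 7 then lists "four analyses examining SUDS, peak GSR (SCR; peak arousal), SCL (tonic arousal), and HF-HRV". For the second of these, "the maximum value of the GSR during the presentation of each sound was used as outcome". No baseline, pre-sound or tonic value is subtracted. The adjustment specific to this outcome is stated in one line: "For SCR, the maximum GSR value during the habituation period was also controlled for". The model also contains group, stimulation condition, block instruction, their interaction, and terms for run order, block position and sound position. SCL is analysed as a block average with baseline values as main effects. Change in GSR from baseline is among the primary outcomes set a priori.

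**The concern.** Within the plan the abbreviation SCR has two meanings. In section 6 it is the spike that is levelled out of the signal. In section 7 it is the maximum of the signal with both spike and tonic level still in it. No phasic amplitude is analysed anywhere, although the plan draws the phasic/tonic distinction itself.

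The tested interaction is group by stimulation by block instruction. If an instruction or a stimulation condition raises tonic arousal during a block, the raw maximum rises even when each sound provokes the same response as before. A reader who sees a result labelled SCR would take it as altered reactivity to sounds. Similar findings for SCR and SCL might also be read as separate evidence on reactivity and on tonic arousal. What is at stake is the interpretation of a primary physiological measure, not the error rate of its test.

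**Working it through.** **1. The plan's own figure.** Four analyses at a family level of .05 give 0.05/4 = 0.0125, as stated. For four independent tests the family-wise error is 1 − (1 − 0.0125)^4 = 0.049. Positive correlation between two of them lowers it further. Re-scoring one outcome leaves four analyses, so the threshold does not change.

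**2. Resolution of the adjustment.** Section 6 gives 3 runs, 5 blocks per run and 4 sounds per block. Each participant therefore has 3 × 5 × 4 = 60 sound maxima, 3 × 5 = 15 block SCL values and 3 habituation maxima. One habituation value serves 5 × 4 = 20 sounds that span all five instruction types. It is the same number for every block of a run, so it cannot carry information on a difference between those blocks.

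**3. What a tonic shift does.** As a simplification, write the maximum for a sound as M = T + A (T tonic level in the block, A response to the sound) and the run's habituation maximum as H. Let T change by D in one block type after habituation, with A unchanged.
- Raw maximum adjusted for H: H is unaffected, so the outcome moves by D.
- Rise score, M minus the tonic level just before the sound: (T + D + A) − (T + D) = A, so it moves by 0.

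A stimulation effect on tonic level that is already present in the 180 s habituation period enters H, because stimulation is on by then. In that case the covariate may absorb part of the stimulation effect.

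**4. Overlap with SCL.** The documents give no GSR variances, so every SD below is an assumption (in microsiemens): between subjects 2 to 4, between runs 0.5 to 1, tonic between blocks 0.1 to 0.6, response 0.2 to 1.0. The simulation used the 3 × 5 × 4 design with 4,000 participants in each of 2 × 2 × 3 × 3 = 36 settings. Both outcomes were centred within subject; the maximum was then regressed on the habituation maximum and SCL on baseline. This approximates the plan's mixed models. Position terms were left out, since the simulated block levels have no average trend for them to remove.

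| Tonic SD between blocks | Adjusted correlation with SCL, per sound |
|---|---|
| 0.1 | 0.09 to 0.30 |
| 0.3 | 0.25 to 0.65 |
| 0.6 | 0.46 to 0.87 |

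For block means the whole range is 0.13 to 0.90. Without any adjustment the per-sound correlation is 0.90 to 1.00.

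**5. Tonic share within a run.** With T and P the SDs of block tonic level and response, share = T²/(T² + P²).
- T = 0.1, P = 0.5: 0.01/0.26 = 4%.
- T = 0.6, P = 0.2: 0.36/0.40 = 90%.

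The documents do not say where in this range the trial lies.

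**The case against.** The strongest defence is that the plan describes the measure openly. It is called peak GSR and peak arousal, beside tonic arousal for SCL, and a raw maximum is a fair measure of peak arousal. The sentence on reactivity concerns GSR as a whole, and the a priori outcome is change in GSR, not phasic amplitude. This stands for the word peak. It does not rescue the abbreviation SCR, which section 6 uses for the component that is removed.

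The design also handles much tonic variation. Repeated measures and the habituation maximum take out much of the stable difference between subjects and runs. Stimulation order and block order are randomised, and run, block and sound position are in the model, so average drift is modelled and is not systematically aligned with condition. This stands too. It leaves a tonic shift caused by the instruction or the stimulation, which none of these features removes. Such a shift may be a real arousal effect, but it is not a larger response to the sound.

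A reader might infer that the SCR analysis largely repeats the SCL analysis, or that tonic level dominates it. The near-perfect unadjusted correlations invite this, but they mostly reflect differences between people and runs that the planned model largely takes out. After adjustment the overlap runs from slight to large. Nor does testing both measures count an effect twice in any sense that breaks the inference: each is tested at .0125, and overlap makes that conservative.

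**Conclusion.** The point holds as a mismatch between label and measure. The outcome called SCR is peak conductance adjusted for one habituation maximum per run. Tonic change within a run that is linked to instruction or stimulation stays in it, so a result on it cannot be attributed to phasic reactivity. This follows from the definitions in sections 6 and 7 and from the additive model, and needs no assumed variance.

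The size in this trial cannot be computed from the documents. The range of about 0.09 to 0.87 for the adjusted per-sound correlation with SCL rests wholly on the assumed SDs and depends mainly on how far tonic level moves between blocks. The documents do not support a claim that the two analyses are redundant, and the .0125 threshold is sound. This is a minor point about what can be concluded; it does not invalidate the test.

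**What to change.** From the continuous recording, score the response as the maximum GSR during each sound minus the level just before that sound, and analyse it in the same model. The sounds take 4 × 25 = 100 s of each 120 s block, so at most 20 s remains for the instruction and any gaps. State the pre-sound window, and check that it is not carrying the tail of the previous response.

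If a pre-sound level cannot be recovered, subtract or adjust for the block SCL, which is already extracted. Say plainly that this leaves drift within the block and removes part of any sustained response to the sounds.

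If the raw maximum is kept, call it peak conductance, report its correlation with SCL, and draw no conclusion about phasic reactivity from it.

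The cost is one derived variable from existing data and a refit. A difference score may be somewhat noisier than the raw maximum. The number of analyses and the threshold stay as they are.

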ID: Pro00103863

Identifying the Optimal Neural Target for Misophonia Interventions

NCT04348591

Study protocol and statistical analysis plan

3/28/2023

Methods:

1. Participants and Procedures

This study was pre-registered under the Clinical Trials ID (NCT04348591) and ran between October 2020 and May 2022. The study was powered based on expected effect size derived from Kumar et al. [2], who compared misophonic participants ($n = 20$) with controls ($n = 22$) to find significant differences in AIC response, with an effect size of 1.27 (mean difference between groups = 2.7 a.u, $SD = 2.11$). For the proposed design, with planned comparisons across condition (downregulate, or listen), sound type (misophonic, aversive, or neutral) and group (misophonic vs. clinical control), and an expected effect size of 1.27, and alpha error rate set at .05, we expected adequate power (over 80%) with 29 participants in each group. Therefore, we aimed to recruit 30 participants in each condition.

Participants were recruited through online websites (e.g., Craigslist, Dukelist), social media (Facebook, Reddit), flyers, and electronic medical record outreach. Participants reached the study predominantly by seeing advertisements on social media and research websites. Many participants who met the severity cutoff for misophonia also found the study via self-guided internet search (see Table 1 for how participants who met the cutoff for each group of interest for the study found the study information).

Table 1. Recruitment methods and success rate in identifying the groups of interest for the study

Recruitment material used	Misophonia participants	Emotion dysregulation participants
Social media (Facebook, Reddit, Instagram)	33.46%	36.42%
Websites (Dukelist, Dukescience, Duke Misophonia website, Dukehealth)	30.08%	28.90%
Word of mouth (friend or medical professional referral)	13.16%	9.83%
Self-guided internet search (including finding the study on clinicaltrials.gov)	12.78%	13.29%
Volunteer registries (BIAC, ResearchMatch, CMER)	6.39%	6.36%
Outreach using electronic medical record	3.38%	4.62%
Newspaper	0.75%	0.58%

Note. Participants were included in the misophonic group if they scored ≥ 2 on the MQ subscales and indicated a severity higher than 6 on the MQ severity scale; participants were included in the emotion dysregulation group if they scored above 89 on the DERS scale.

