Preliminary analyses, including *t*-tests and chi-squares, were conducted to assess demographic differences between experimental groups. We also examined any differences on matching variable (sex at birth, age) and other potential confounding variables like demographic characteristics, use of medication, dissociation during the experimental task, sleepiness during the experimental day, discomfort during neurostimulation, or psychophysiological effects induced by rTMS alone.

Primary outcomes set *a priori* were BOLD signal differences within the dlPFC and vmPFC during regulation of misophonic versus aversive sounds, BOLD signal differences within the AIC when listening to misophonic versus aversive sounds, change in HF-HRV and GSR during experimental blocks from baseline, acceptability of procedures as measured by percent of participants who complete the sessions. Secondary outcomes included self-reports (SUDS during the neurostimulation experiment, DERS, PROMIS-43), whole-brain BOLD changes when comparing aversive with neutral sound presentation and regulation, and when comparing misophonic with neutral sounds presentation and regulation.

To examine differences in functional activation between groups during the neuroimaging experiment, a group analysis was performed. Each functional and PPI FSL Level 2 analysis for each participant was entered into a third level FSL FEAT analysis assessing the differences between participants who in either the misophonia or the clinical control group.

To compare groups on functional connectivity during contrasts that were not included for targeting, four additional whole brain PPI analyses were performed using the same left insula seed, thresholded at 2.3, and then using the time series from this anatomical mask as the physiological regressor. In addition to the functional task regressors, each additional PPI analysis included one of the contrasts of interest as

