regressors: [listen to misophonic vs. aversive sounds], [downregulate vs. listen to misophonic sounds], [listen to aversive vs. neutral sounds], and [downregulate vs. listen to aversive sounds]. For all, the PPI was defined as the interaction between this event and the physiological regressor (66, 67). This method was performed for each subject and for each run. A third level analysis was then performed to assess the differences between groups. PPI analyses probe the synchronization of brain activity between two brain regions allowing us to differentiate regions which interact with each other versus work independently during experimental tasks (68). Whole brain Z image statistics (from both functional and PPI analyses) were thresholded using clusters determined by $Z > 2.3$ and a corrected cluster significance of $p = .05$ (69). Mixed-effects hierarchical linear models (MMANOVA) with analytically determined covariance structures were used to analyze the repeated measures data (70). All MMANOVA models used a restricted estimated maximum likelihood model to account for missing data (71) (i.e., cases with missing data were not discarded, but slopes for each participant were computed with the data available). Estimated marginal means (EMMs) were compared using LSD corrections for significant main and interaction effects, and are presented in the results section. For data that was not repeated, independent sample t -tests or non-parametric equivalents were employed. To test the neurobiological basis of misophonia, correlation analyses with neuroimaging data extracted from regions of interest (ROIs) and baseline behavioral measures were employed.

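### The multiplicity correction does not follow the plan's primary list: it includes secondary SUDS, while the BOLD primaries have no control across contrasts or against the psychophysiological primaries

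*Combined protocol and SAP*

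**What the plan says.** All the relevant statements are in Section 7, Statistical Analyses, of the combined protocol and SAP.

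- **Primary outcomes, imaging.** Two statements: "BOLD signal differences within the dlPFC and vmPFC during regulation of misophonic versus aversive sounds" and "BOLD signal differences within the AIC when listening to misophonic versus aversive sounds".
- **Primary outcomes, other.** Change in HF-HRV and in GSR from baseline, and acceptability measured by the percentage completing the sessions.
- **Secondary outcomes.** "Secondary outcomes included self-reports (SUDS during the neurostimulation experiment, DERS, PROMIS-43", followed by whole-brain comparisons against neutral sounds.
- **Imaging threshold.** Whole-brain maps use Z > 2.3 with "a corrected cluster significance of $p = .05". No adjustment is stated across contrasts or regions, and no threshold is given for a region-level test.
- **Neurostimulation analyses.** The plan says "we conducted four analyses examining SUDS, peak GSR (SCR; peak arousal), SCL (tonic arousal), and HF-HRV", and then "To account for multiple comparisons, we used a Bonferroni correction, and dropped the significance threshold to .0125".

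The plan does not say whether the imaging and psychophysiological primaries form one family or two.

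**The concern.** A multiplicity correction should protect the claims that the plan itself calls primary. Here the corrected set and the primary set overlap only in part. SUDS, a declared secondary outcome, holds one of the four shares of alpha. The BOLD primaries hold none, and the imaging control works only inside each map. Nothing in the plan requires more than one primary to succeed, so a positive result on any of them could be presented as a primary finding, with no stated limit on the chance that at least one is false.

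A reader also cannot tell whether .0125 is too strict or too lenient for HF-HRV and GSR. That depends on a family structure the plan never declares.

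**Working it through.** **1. The plan's figure.** Section 1 sets alpha at .05, and Section 7 names four neurostimulation analyses. .05/4 = .0125, which reproduces the stated threshold exactly. SUDS is therefore one of the four.

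**2. Assumptions.**
- Tests are independent.
- Each BOLD primary or map is tested at .05. Section 7 gives that level for whole-brain maps only.
- Each analysis counts as one test.
- Acceptability is left out, because no hypothesis test is described for it.

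**3. Chance of at least one false-positive primary.** With b BOLD tests at .05 and p psychophysiological tests at .0125, the chance is 1 − .95^b × .9875^p. The union bound is .05b + .0125p. Here p = 3 if GSR is analysed as SCR and SCL, as in Section 7, and p = 2 if GSR counts once.

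| BOLD tests | p | Calculation | Independent | Union bound |
|---|---|---|---|---|
| 2 (one regulation map, one listening map) | 2 | 1 − .9025 × .9752 | 12.0% | 12.5% |
| 2 | 3 | 1 − .9025 × .9630 | 13.1% | 13.75% |
| 3 (dlPFC, vmPFC, AIC) | 2 | 1 − .8574 × .9752 | 16.4% | 17.5% |
| 3 | 3 | 1 − .8574 × .9630 | 17.4% | 18.75% |

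Imaging alone gives 1 − .95² = 9.75% with two maps and 1 − .95³ = 14.3% with three tests.

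**4. How far the two-map figures can be relied on.** A cluster-corrected level of .05 covers a false cluster anywhere in the brain. A claim about a named region is narrower, so these figures are upper bounds for it. The three psychophysiological tests alone use 1 − .9875³ = 3.7%. The total passes 5% once imaging contributes more than 1 − .95/.9630 = 1.3% (with p = 2, 1 − .95/.9752 = 2.6%).

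**5. Is .0125 too strict or too lenient for HF-HRV and GSR?**

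| Family structure | Bonferroni threshold | .0125 is |
|---|---|---|
| Psychophysiology separate, SUDS removed, three measures | .05/3 = .0167 | too strict |
| Psychophysiology separate, SUDS removed, two outcomes | .05/2 = .025 | too strict |
| One family, three BOLD and three psychophysiological | .05/6 = .0083 | too lenient |
| One family, five tests (3 + 2 or 2 + 3) | .05/5 = .0100 | too lenient |
| One family, two BOLD and two psychophysiological | .05/4 = .0125 | equal by coincidence |

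The last row needs GSR to be one test, whereas Section 7 analyses it as two.

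**6. Effect on power.** The plan gives no power figure for HF-HRV or GSR, so this is illustrative. By the normal approximation, a two-sided test with 80% power at .0125 has 82.8% at .0167 and 86.4% at .025, but 77.7% at .0100 and 75.8% at .0083.

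**The case against.** The best defence is that the correction has a stated scope. The four analyses compare neurostimulation conditions. The BOLD outcomes address another question, group differences in an earlier MRI session, with their own cluster correction, and Section 5 says the full fMRI analyses are to be presented elsewhere. Correcting by research question is a defensible choice, and including SUDS cannot inflate type I error. Loosening a threshold after the data are in could also be worse than keeping a conservative one.

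Much of this stands. It explains how the plan reached four, and it makes the loss from including SUDS small. It does not explain why a secondary outcome shares alpha with primaries, and it leaves the regulation and listening contrasts without joint control even within imaging. Where results are published does not define the error family.

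A reader might infer three stronger points that the documents do not support:

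- **The primaries are under-controlled because BOLD was left out, and HF-HRV and GSR are over-penalised as well.** These cannot both follow from a single family: adding the three BOLD outcomes lowers the threshold to .0083–.0100.
- **The BOLD primaries are uncorrected.** They have within-map cluster correction.
- **The false-positive chance is about 22%.** This figure, 1 − .95⁴ × .9875³ = 21.6%, needs two contrasts each tested in both directions at .05, and the plan does not state that.

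**Conclusion.** The mismatch between the corrected set and the primary list can be read directly from Section 7. Under the assumptions in the working, the chance of at least one false-positive primary is about 12–13% when dlPFC and vmPFC share one map, which is natural because they share one contrast. It is up to about 17% when three BOLD tests are counted, a count that treats the regions as separate tests although no such tests are specified. Region-specific claims from maps would carry less error than the map figures. Section 7 also compares estimated marginal means by LSD, which makes no multiplicity adjustment; that and several effects per model could add error not counted here.

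That the primaries exceed 5% is a fault only if they are read as one set of claims, which the plan neither affirms nor denies. Over-penalisation of HF-HRV and GSR is conditional on separate families with SUDS removed, and it is modest. The main defect is that the family structure is undeclared and the imaging primaries have no cross-contrast control.

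**What to change.** 1. Declare imaging and psychophysiology as two separate primary claims, each at .05 with Holm. Imaging covers the regulation and listening outcomes; psychophysiology covers HF-HRV, SCR and SCL. State that this bounds the error across both at .05 + .05 = 10% (1 − .95² = 9.75% if independent). If a single 5% claim is intended, use one Holm family over all of them.
2. State how each BOLD primary is tested: by whole-brain map or by region, in which direction and at what level. This settles whether imaging has two tests or three.
3. Report SUDS as secondary, without a confirmatory claim.
4. Report adjusted p-values.
5. The study ended in May 2022 and the document is dated March 2023, so label the change as post hoc and show the neurostimulation results at the stated .0125 alongside.

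If the sponsor prefers to leave SUDS in the set of four, Holm in place of Bonferroni keeps the same error control and is never less powerful. The imaging step is still needed.

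The cost is SAP wording and recalculated p-values, with no new data. The downside is a stricter threshold for the BOLD findings: the smallest p-value would face .05/2 = .025 with two imaging tests, or .05/3 = .0167 with three.
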